## **10.7.2 S-ICD Evaluation**

#### 10.7.2.1 S-ICD Summary Report

It is required to retain the "S-ICD Summary Report" from the programmer, documenting initial and final parameter settings, episode counters, battery status, etc. Note whether MRI Protection Mode was programmed "On" since the previous protocol-required visit; if it was, report this in EDC in the Medically Necessary MRI Scan page.

#### 10.7.2.2 Spontaneous Episodes

All available "Full S-ECG Report(s)" and "Full S-ECG Report(s) Untreated" (AF diagnostic episodes labeled "Full S-ECG Report AF" are not required) not previously reported must be obtained and uploaded to BSC via the EDC System. Documentation of any symptomatic episodes associated with a spontaneous event will be collected, specifically any syncope. Justification shall be provided for any missing episodes.

#### 10.7.3 mCRM Coordinated System Testing

#### 10.7.3.1 Four-Posture Communication Test

Perform communication testing in each of the 4 postures included in Figure 10-2, It is recommended to test postures in the order presented in Figure 10-2. Document the order of postures on the appropriate Technical Source Form.

Figure 10-2: Recommended Order of Postures for Four-Posture Communication Test

## 10.7.3.2 Communication Test

A single Communication Test is required to be performed at the initial programmed Telemetry Setting in each of the four postures noted in **Figure 10-2**. In the event that multiple communication tests are performed within a posture, only the first Communication Test S-ECG Report obtained at the initial programmed Telemetry Setting will serve as the source document for the endpoint. All required testing should be completed in the selected posture before changing to another posture.

In the event of a communication failure in one or more of the four postures during the single test, perform a Communication Threshold Test (described in **Section 10.3.4.5**) in the posture(s) of communication failure. Use the highest value to program the Telemetry Setting output 1 unit above threshold among all tested posture(s). For example, if the threshold is 5, program the output to 6.

## 10.7.4 mCRM Coordinated System Programming

Recommended programming parameters for the EMPOWER PG and S-ICD are included in **Sections 10.4.4.1** and **10.4.4.2**, respectively.

Print out a copy of the final "Combined Follow-up Report" and a copy of the "S-ICD Summary Report". Once all study activities are completed at the end of the visit, reset the EMPOWER PG brady counters/ histograms and tachy counters.

# 10.7.5 6 Month Visit Source Documentation Requirements

6 Month Visit data and source documentation requirements are listed in Table 10-14.

Data Collection	Retention of Original Source Documentation
EMPOWER Programmer Reports: - Initial EMPOWER Combined Follow-up Report - EMPOWER Real-Time Log Report (to document LOC) - Final EMPOWER Combined Follow-up Report	Study site
S-ICD Programmer Reports: - S-ICD Summary Report from the end of the visit - Full S-ECG Report(s) Treated, if applicable - Full S-ECG Report(s) Untreated, if applicable 	Study site; upload copy to BSC via study EDC system

 
Communication Test S-ECG Reports, including Communication Test (Threshold) S-ECG Reports, if conducted
 
Order of postures tested documented on TSF
 
	Study site
Reportable Adverse Events, Device Deficiencies, and Protocol Deviations, if applicable	Study site
Data items that do not have an original source document will be collected on a TSF	Study site

## Table 10-14: 6 Month Visit Data Collection Requirements

#### 10.8 Semi-Annual Visits

Semi-Annual Visits are required to be conducted as clinic visits for MODULAR ATP subjects, starting at 12 months post mCRM Coordinated System implant and continuing until study closure. Note subjects are required to be followed until the last enrolled subject is followed for at least 24 months post mCRM Coordinated System implant. Timing of the Semi-Annual Visits is based on the date the mCRM Coordinated System was fully implanted:

- 12 Month: 360±45d
- 18 Month: 540±45d
- 24 Month: 720±45d
- 30 Month: 900±45d
- 36 Month: 1080±45d
- Etc, until BSC notification of follow-up completion

<sup>30 Note that AF diagnostic episodes labelled "Full S-ECG Report AF" are NOT required.

## **10.8.1 EMPOWER PG Evaluation**

PCT, Pacing Impedance, and R-wave Amplitude are required to be measured. Collect PCT measurements according to **Section 10.3.1.7**.

It is required to retain the "Real-Time Log Report" from the programmer, documenting at a minimum the LOC portion of the threshold testing (i.e., the lowest voltage setting demonstrating capture and the highest voltage setting that fails to capture). This documentation will be retained at the study site.

If more than one set of electrical measurements are recorded, the final set must be used for the study.

It is required to document the following:

- "%V paced" from the "Combined Follow up Report",
- "Time remaining to EOS" from the "Combined Follow up Report",
- "Charge remaining to EOS" documented on the TSF.

## **10.8.2 S-ICD Evaluation**

#### 10.8.2.1 S-ICD Summary Report

It is required to retain the "S-ICD Summary Report" from the programmer, documenting initial and final parameter settings, episode counters, battery status, etc. Note whether MRI Protection Mode was programmed "On" since the previous protocol-required visit; if it was, report this in eDC in the MRI Scan page.

#### 10.8.2.2 Spontaneous Episodes

All available "Full S-ECG Report(s)" and "Full S-ECG Report(s) Untreated" (AF diagnostic episodes labeled "Full S-ECG Report AF" are not required) not previously reported must be obtained and uploaded to BSC via the EDC System. Documentation of any symptomatic episodes associated with a spontaneous event will be collected, specifically any syncope. Justification shall be provided for any missing episodes.

#### 10.8.3 Communication Test in One Posture

A single Communication Test is required to be performed at the initial programmed telemetry value with the subject in one selected posture. The upright posture shown in **Figure 10-2** is recommended, but the posture to be used is at the physician's discretion. For example, a different posture might be appropriate for subjects in which the highest mCRM communication threshold has been observed for a different posture or for subjects that have experienced ambulatory VT events in another posture. The actual posture tested must be recorded. In the event that multiple communication tests are performed within the selected posture, only the first "Communication Test S-ECG Report" obtained at the initial programmed Telemetry Setting value will serve as the source document for the test. Refer to the mCRM PTM, as well as **Section 10.3.4.2** to prepare for a Communication Test. Follow Communication Test methodology in **Section 10.3.4.4**.

In the event of a communication failure in the selected posture during the single test, perform a Communication Threshold Test in the selected posture; refer to **Section**

**10.3.4.5**. Use the resulting value from that test to program the Telemetry Setting output 1 unit above threshold. For example, if the threshold is 5, program the output to 6.

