## 10.3.4.5 Communication Threshold Test

Assure the EMPOWER PG and S-ICD PG are set up for communication testing as described in **Section 10.3.4.2**.

There are no requirements for the Telemetry Setting value used to start this test. Choose a Telemetry Setting value to start the Communication Threshold Test. If successful, then step down incrementally by 0.5, and repeat the test. Continue stepping down by 0.5 and

Page 54 of 148

repeating the test until an unsuccessful test occurs. After having a single unsuccessful test, step up by 0.5 and repeat the test as needed until success is achieved. The communication threshold is recorded as the minimum value that achieves two successful tests, regardless of sequence.

It is required to retain the "Communication Test S-ECGs" documenting the maximum Telemetry Setting value demonstrating loss of communication, as well as the minimum Telemetry Setting value that achieves two successful tests. This documentation will be retained at the study site.

Program the communication Telemetry Setting value 1 unit above the highest communication threshold value among all tested postures as applicable, with a minimum Telemetry Setting of 4. For example, if the threshold is 5, program the output to 6.

**Note:** If intrinsic rhythm is not present, pacing pulses in response to a communication request will not be delivered because a sensed beat is required.

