## Figure 10-1: Recommended Order of Postures for Four-Posture Communication Threshold Test

## 10.5.3.2 Communication Threshold Test

Communication Threshold Testing is required at the 1 Month Visit with the subject in each posture noted in **Figure 10-1**.

Refer to the mCRM PTM, as well as **Section 10.3.4.2** to prepare for a Communication Threshold Test. Follow Communication Threshold Test methodology in **Section 10.3.4.5**. All required testing should be completed in the selected posture before changing to another posture.

Program the communication telemetry output 1 unit above the highest communication threshold value among all tested posture(s), with a minimum *Telemetry Setting* of 4. For example, if the threshold is 5, program the output to 6.

**Note:** If intrinsic rhythm is not present, pacing pulses in response to a communication request will not be delivered because a sensed beat is required.

**Note:** Since pacing has the potential to interfere with communication, it is recommended to select Off for the mCRM Communication Test backup pacing setting. However, if the subject is pacemaker dependent, configure the backup pacing mode at the lowest pacing rate needed for the subject, preferably 50 ppm or lower, for the duration of the Communication Test.

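### After a failed single-posture Communication Test, Protocol 10.8.3 resets the Telemetry Setting from that posture alone, so a failure that does not repeat can lower the output below another posture's 1 Month threshold

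*Protocol*

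**What the plan says.** **1 Month.** Protocol 10.5.3.2 requires a threshold test in each of four postures and sets the output from the worst of them: "Program the communication telemetry output 1 unit above the highest communication threshold value among all tested posture(s"), with a minimum of 4.

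**General method.** Section 10.3.4.5 defines the result: "The communication threshold is recorded as the minimum value that achieves two successful tests, regardless of sequence". It sets the output at "1 unit above the highest communication threshold value among all tested postures as applicable, with a minimum Telemetry Setting of 4".

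**Semi-Annual Visits.** Section 10.8.3 requires one Communication Test in one posture. Upright is recommended, but the physician may choose another. If the test fails, a threshold test by 10.3.4.5 follows in that posture, and then: "Use the resulting value from that test to program the Telemetry Setting output 1 unit above threshold". Section 10.9 sends Additional Visits for communication-related adverse events to the same procedure.

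**6 Months.** Section 10.7.3.2 tests all four postures once at the programmed setting. A threshold test follows only "in the posture(s) of communication failure", and the output is then reset ("Use the highest value to program the Telemetry Setting output 1 unit above threshold among all tested posture(s").

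Neither 10.8.3 nor 10.7.3.2 mentions the setting in force or the thresholds already recorded for the other postures.

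**The concern.** The protocol tests four postures because device orientation affects communication (6.6), and the 1 Month rule protects the worst posture. The reset in 10.8.3 replaces that four-posture maximum with a one-posture value.

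If the failure repeats, the new threshold lies above the old setting and the output rises, as intended. If it does not repeat, the retest can return a low threshold, and the written instruction then lowers the output for every posture.

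The Telemetry Setting affects whether an ATP request reaches the pacemaker, so the possible cost is a missed ATP request in a posture that was not retested. It might also go unnoticed: Table 10-6 requires no four-posture test after 6 Months, and a subject could pass each later upright test at the lowered setting. The SAP (1.3) summarises Semi-Annual Communication Tests and communication during spontaneous episodes, and those ancillary results would be the ones touched.

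**Working it through.** **Inputs.** The programmable settings run from 1 to 7 in steps of 0.5 (25.2). The margin is 1 unit and the floor is 4 (10.3.4.5, which 10.8.3 cites). Let S be the setting in force, T the threshold found on retest, and N the new output.

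**Rule.** N = max(4, T + 1). The plan's own example is reproduced: T = 5 gives N = 6.

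**Example.**
- 1 Month thresholds are upright 2 and supine 5, so S = max(2, 5) + 1 = 6.
- At 12 months the upright test fails once at 6. The upright threshold test again gives 2.
- N = max(4, 2 + 1) = 4, which is 5 − 4 = 1 unit below the supine 1 Month threshold.

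**All combinations.** Take S from 4 to 7 (7 values) and T from 1 to 6 (11 values, so that T + 1 can be programmed). That gives 7 × 11 = 77 pairs. Under the 1 Month rule, S − 1 stands for the worst-posture threshold when S is above 4.

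| S | pairs with N < S | of these, N < S − 1 |
|---|---|---|
| 4 | 0 | 0 |
| 4.5 | 5 | 0 |
| 5 | 6 | 0 |
| 5.5 | 7 | 5 |
| 6 | 8 | 6 |
| 6.5 | 9 | 7 |
| 7 | 10 | 8 |
| Total | 45 | 26 |

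- In the 45 pairs the output drops by 0.5 to 3 units.
- In the 26 pairs the shortfall below S − 1 is 0.5 (8 pairs), 1.0 (7), 1.5 (6) or 2.0 (5).
- In the remaining 45 − 26 = 19 pairs the output stays at or above S − 1, but the margin falls from 1 unit to 0 (9 pairs) or 0.5 (10 pairs).

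**Second layout.** Take the retested posture's threshold a and the highest other-posture threshold b, each from 1 to 6, giving 11 × 11 = 121 pairs. The output is lowered in 45 and falls below b in 26. The latter needs b of at least 4.5 and a at least 1.5 below b.

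**With the fix.** N = max(4, S, T + 1) is never below S, so 0 of 77 pairs lower the output. In the second layout 0 of 121 fall below b.

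These counts show what the rule allows. They are unweighted and are not probabilities.

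**The case against.** **Section 10.7.3.2 is less clear.** All four postures are tested at 6 Months, and the phrase about all tested postures means all four in 10.5.3.2. A reader might infer that 10.7.3.2 plainly resets from the failed postures alone. It does not say so plainly. That is still the natural reading, because only failed postures get a new threshold at that visit. The postures that passed have been shown to work at the old setting, not at a lower one.

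**The comparator may be stale.** The 1 Month threshold is measured at day 10 to 42 and not again unless a test fails. A reader might infer that an output below it means lost communication. The documents do not show that; they show only that the margin against the last recorded value is gone.

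**S − 1 is not always the worst-posture threshold.** It need not be so at 7, where thresholds of 6.5 or 7 would also be programmed at the maximum, or after a later reset. If the retested posture is itself the worst, there is no shortfall against another. This is a further reason not to read the counts as sizes of risk.

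**Several conditions must coincide.** The planning value of 95% communication success implies that about 5% of 6 Month tests fail, and only failures that do not repeat matter here. A test without a sensed beat may be repeated as the official result (10.3.4.1). The physician may choose the worst posture or test further. The retained record must show "the maximum Telemetry Setting value demonstrating loss of communication", which could prompt caution. All this makes the event less likely. It does not change the instruction: no sentence lets that recorded loss limit the reset, and Section 14 forbids deviation except in an emergency.

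**The free start value does no work.** Section 10.3.4.5 says "There are no requirements for the Telemetry Setting value used to start this test", and a reader might blame that. In the example, starting at 6 or 7 and stepping down still gives 2.

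**The mCRM technical manual was not available.** It may address lowering the setting. The protocol should not direct a lower output in either case.

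**Conclusion.** The point holds as a minor one. The text of 10.8.3, and through it 10.9, supports it directly; 10.7.3.2 supports it on its most natural reading. If a failure does not repeat, the output can end 0.5 to 2 units below the worst-posture threshold implied by the 1 Month rule when the setting in force is 5.5 or more. At 4.5 or 5 only the margin shrinks, and at 4 the output cannot be lowered.

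This assumes that the floor of 4 applies by cross-reference, that the setting in force came from the 1 Month rule, and that another posture is the worst one. The documents do not say how often a failure does not repeat, so no frequency follows.

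A reader might also infer that Primary Effectiveness Endpoint 1 is biased. It is not: 10.7.3.2 takes the endpoint from the first test in each posture at the initial programmed setting, before any reset. No other primary or secondary endpoint is affected. What remains is individual device programming, the ancillary communication summaries, and a possibly missed ATP request with S-ICD shock therapy still in place.

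**What to change.** In 10.8.3 and 10.7.3.2, after the instruction to program 1 unit above threshold, add: *but not below the setting in force before the failed test, unless all four postures have new thresholds at that visit.* The exception permits a lower output when a complete new set of thresholds supports it. In 10.7.3.2 the clause also makes the ambiguity harmless. Additional Visits are covered through the existing reference to 10.8.3, and restating the minimum of 4 is optional.

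The cost is one clause in two sections, with no extra test, visit or data field; the S-ICD Summary Report already documents initial and final settings. The downside is that some subjects keep an output already in use, with its battery use and any muscle stimulation, where a lower one might have sufficed. Muscle stimulation is checked up to the maximum of 7, but only at Implant (10.3.4.3), so that check gives limited reassurance later on.

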#### 10.8.4 mCRM Coordinated System Programming

Therapy zone and ATP settings are to be programmed per **Table 10-9** for primary prevention subjects and **Table 10-10** for secondary prevention subjects. All other programming parameters (e.g., sensing vector, gain) are left to the discretion of the investigator. Rationale for not following the recommended programming parameters will be collected.

Recommended Programming Parameters for the EMPOWER PG and S-ICD are included in **Sections 10.4.4.1** and **10.4.4.2**, respectively.

Print out a copy of the final "Combined Follow-up Report" and a copy of the "S-ICD Summary Report". Once all study activities are completed at the end of the visit, reset the EMPOWER PG brady counters/ histograms and tachy counters.

#### 10.8.5 Semi-Annual Visit Source Documentation Requirements

Semi-Annual Visit data and source documentation requirements are listed in Table 10-15.

Data Collection	Retention of Original Source Documentation	
EMPOWER Programmer Reports: - Initial EMPOWER Combined Follow-up Report - EMPOWER Real-Time Log Report (to document loss of capture) - Final EMPOWER Combined Follow-up Report	Study site	
S-ICD Programmer Reports: - S-ICD Summary Report from the end of the visit - Full S-ECG Report(s) Treated, if applicable - Full S-ECG Report(s) Untreated, if applicable 	Study site; upload copy to BSC via study EDC system	
Communication Test S-ECG Report(s), including Communication Test (Threshold) S-ECG Reports, if conducted	Study site	
Reportable Adverse Events, Device Deficiencies, and Protocol Deviations, if applicable	Study site	
Data items that do not have an original source document will be collected on a TSF	Study site	

#### Table 10-15: Semi-Annual Visit Data Collection Requirements

#### 10.9 Additional Visits

Additional Visits must be collected if they are associated with a reportable adverse event, spontaneous episode, or device deficiency. Routinely scheduled office visits for purposes other than these events, do not require Additional Visit forms to be completed.

In the event of an adverse event related to communication of the mCRM Coordinated System, a Communication Test, and possibly a Communication Threshold Test (as described in **Section 10.8.3**) is required. In the event of an adverse event related to the EMPOWER device, an evaluation of that device is required as described in **Section 10.3.1.7**.

#### **10.9.1 EMPOWER PG Evaluation**

Device evaluation is optional at these visits. If performed, collect PCT measurements according to **Section 10.3.1.7**, except that a pulse width of 0.4 ms is recommended.

It is required to document the following:

<sup>31 Note that AF diagnostic episodes labelled "Full S-ECG Report AF" are NOT required.

<sup>32 Refer to Section 25.2 for definition of reportable adverse event

- "%V paced" from the "Combined Follow up Report",
- "Time remaining to EOS" from the "Combined Follow up Report",
- "Charge remaining to EOS" documented on the TSF.

### 10.9.2 S-ICD Evaluation

#### 10.9.2.1 S-ICD Summary Report

It is required to retain the "S-ICD Summary Report" from the programmer, documenting initial and final parameter settings, episode counters, battery status, etc. Note whether MRI Protection Mode was programmed "On" since the previous protocol-required visit; if it was, report this in eDC in the MRI Scan page.

#### 10.9.2.2 Spontaneous Episodes

All available "Full S-ECG Report(s)" and "Full S-ECG Report(s) Untreated" (AF diagnostic episodes labeled "Full S-ECG Report AF" are not required) not previously reported must be obtained and uploaded to BSC via the EDC System. Documentation of any symptomatic episodes associated with a spontaneous event will be collected, specifically any syncope.

**Note:** any spontaneous stored episodes that occurred prior to enrollment should not be reported. Justification shall be provided for any missing episodes.

Print out a copy of the final "Combined Follow-up Report" and a copy of the "S-ICD Summary Report". Once all study activities are completed at the end of the visit, reset the EMPOWER PG brady counters/ histograms and tachy counters.

#### 10.9.3 Additional Visit Source Documentation Requirements

Additional Visit data and source documentation requirements are listed in Table 10-16.

Data Collection	Retention of Original Source Documentation	
EMPOWER Programmer Reports: - Initial EMPOWER Combined Follow-up Report - EMPOWER Real-Time Log Report (to document loss of capture), if applicable - Final EMPOWER Combined Follow-up Report	Study site	
S-ICD Programmer Reports: - S-ICD Summary Report - FULL S-ECG Report(s) Treated, if applicable - Full S-ECG Report(s) Untreated, if applicable 	Study site; upload copy to BSC via study EDC system	
Communication Test S-ECG Report(s), if applicable, including Communication Test (Threshold) S-ECG Reports, if conducted	Study site	
Reportable Adverse Events, Device Deficiencies, and Protocol Deviations, if applicable	Study site	
Data items that do not have an original source document will be collected on a TSF	Study site	

### Table 10-16: Additional Visit Data Collection Requirements

# 10.10 Medically Necessary MRI Scans

During the MODULAR ATP Clinical Study, if a subject requires a medically necessary MRI scan, BSC recommends the subject be directed to have the scan at the study site.

The investigational EMPOWER PG is MR Conditional during the course of the clinical study, as is the mCRM System. Labeled recommendations for device testing included in relevant PTMs will be collected in the MODULAR ATP Clinical Study, as well as any adverse events that may occur. Refer to "mCRM and EMPOWER MRI Tech Guide" for the Conditions of Use for the mCRM System, and programming recommendations for the EMPOWER PG. Refer to the S-ICD MRI Tech Guide for programming guidance for the S-ICD during the scan.

Based on the PTMs listed above, collect the following data prior to and after the MRI Scan:

• PCT (refer to **Section 10.3.1.7**), pace impedance, and sensed amplitude from the EMPOWER PG

<sup>33 Note that AF diagnostic episodes labelled "Full S-ECG Report AF" are NOT required.

MODULAR ATP

• Communication Test in a single posture (refer to Section 10.3.4.2 and Section 10.3.4.4). It is recommended to use the same posture for the pre- and post-MRI scan Communication Test.

• PMST (refer to Section 10.3.4.6)

